### **2.3 – Study Design**

We propose a prospective, randomized, controlled trial comparing insufflation pressures during RALP. Standard pressure is typically 15 mmHg, while in our previous study we determined that 6 mmHg is possible routinely; therefore, we plan to compare the clinical outcomes of patients between pneumoperitoneal pressures. Potential study subjects will be identified by reviewing clinic schedules at the PI's Robotic Urology practice at Dublin Methodist Hospital. As part of the new patient paperwork, patients will be mailed an informational letter (see Appendix G) highlighting active research studies for review prior to the index routine visit with the PI.

All patients that are candidates for RALP will be screened by the Clinical Research Coordinator (CRC) prior to their surgery planning visit. Once a patient is identified as meeting all study criteria, they will be approached by the CRC at their visit and the study will be thoroughly explained. After the patient has had all their questions answered and has agreed to participate in the study, informed consent will be obtained, followed by randomization in a 1:1 single-blinded fashion to either a pneumoperitoneal insufflation pressure of 15 mmHg (control group) or 6 mmHg (study group). The randomization allocation schedule will be developed by staff from the OhioHealth Research & Innovation Institute (OHRI), and will be hidden from the investigators until directly prior to surgery to prevent bias. Specifically, the CRC will open the randomization envelope in the operating room (OR) immediately prior to surgery. Randomization will be blocked to prevent selection and accidental bias.

Patients will be prepared for surgery per standard institutional policy and routine practice; the only difference in surgical technique will be the insufflation pressure applied. All ports will be placed

according to routine care using the AirSeal iFS, and all clinical decisions will be made per standard practice and policy. [name] (the PI) will be the only surgeon performing these procedures, eliminating any variation in technique between surgeons. Participants in this study are not exposed to any additional or different risks associated with the surgery, as all patients will undergo insufflation. Following trocar placement, initial insufflation will be performed at 6 mmHg for patients in the study group and 15 mmHg for patients in the control group. If required, insufflation pressures for the study group will be increased up to 15mmHg per standard surgeon protocol. Increased insufflation pressure will be maintained either transiently (≤5 minutes to control bleeding or to improve access/visualization) or for the duration of the procedure as per surgeon need. The amount of time at each insufflation pressure will be recorded.

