### **1.2 – Specific Aims/Rationale**

We propose a study comparing insufflation pressures during RALP. Standard pressure is typically 15 mmHg, while in our previous study we determined that 6 mmHg is possible routinely. Therefore, we plan to compare the clinical outcomes of patients at a pneumoperitoneal pressure of 15 versus 6 mmHg.

***Aim #1)*** Compare average postoperative pain medication use between groups, as measured in total morphine equivalents (MME) over time at pre-specified time intervals through follow-up at 1 week.

***Aim #2)*** Compare average and maximum postoperative pain scores between groups, as measured using the self-reported 11-point numerical rating scale (NRS), over time at pre-specified time intervals through discharge.

Time intervals for Aims #1 & 2 are as follows: during the post-anesthesia care unit (PACU) stay, the first 4 hours on the floor, next 8 hours, and the following 8 hours; as well as the final score immediately prior to discharge.

***Aim #3)*** Compare operative ventilation as measured by average tidal volume (ml) between groups.

Tidal volume is the lung volume representing the normal volume of air displaced between normal inspiration and expiration when extra effort is not applied (i.e., normal/resting breathing), and is measured continuously throughout the procedure by Anesthesia. Potential patient benefits to a lower pneumoperitoneal insufflation pressure include decreased postoperative pain and improved intraoperative ventilation.

***Aim #4)*** Compare average length of stay (typically 0-1 days) between groups.

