**Table 2. Post-operative pain monitoring schedule.**

Timeframe	Description	Time-Points	Pain Locations
During PACU stay	Upon admission to the PACU (typical stay of 1-2 hours)	PACU	Abdomen Legs
1 st 4 hours on the floor	Every 2 hours during the first 4 hours on the floor	Floor-0, 2, & 4 (hours 0 through 4)	Groin Scrotum
Next 8 hours on the floor	Every 2 hours during the next 8 hours on the floor	Floor-6, 8, 10, & 12 (hours 5 through 12)	Shoulder
Following 8 hours on the floor	Every 2 hours during the following 8 hours on the floor	Floor-14, 16, 18, & 20 (hours 13 through 20)	Other/specify
Final score immediately prior to discharge	Recorded on the floor prior to discharge; OR via phone call by CRC for those discharged same-day	Discharge, or Post-discharge	

1-Scores measured only while inpatient (or post-discharge for those discharged same-day) and awake; measures not taken in <1 hour from planned time will be marked as "missed."

Pain scores are measured using an 11-point numerical rating scale (NRS), in which a rating of 0 corresponds to no pain, 1-3 indicates mild pain, 4-6 indicates moderate pain, and 7-10 corresponds to severe pain. Scores are recorded by nursing staff as part of routine care in the PACU and on the postoperative recovery floor during the inpatient stay, however these measures are often not recorded in a consistent fashion with respect to timing. Therefore, we will record scores every 2 hours during the inpatient stay while the patient is awake (with the exception of the PACU, which occurs only at admission), and determine the average and maximum scores reported over sequential timeframes: during the PACU stay (typical stay of 1-2 hours), the first 4 hours on the floor, next 8 hours, and the following 8 hours; as well as the final score immediately prior to discharge (see Table 2). There will be no strict time window due to the variability of sleep schedules and discharge timing during the short inpatient stay, however, scores will be marked as "missed" if not recorded in <1 hour of the planned time. Pain will be measured with respect to the abdomen, legs, groin, scrotum, shoulder (due to insufflation), and "other" location. Pain medication morphine equivalents (MME) will also be measured over the same sequential timeframes during the inpatient stay through 1 week postoperatively. Patients

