will be educated on the importance of bringing all medications to follow-up visits, which will lead to more accurate pain medication counts and calculations.

Patients are typically discharged on Day 0-1, and for those discharged on Day 0 (i.e., same-day), the CRC will call the following morning to evaluate pain (see Appendix C). Because we are targeting same-day or next-day discharge, there is the potential for missing data in the first 24-hour period. Therefore, there will be no restrictions or protocol deviations for pain scores, as we are collecting scores only while inpatient/awake and via phone call for those discharged same-day. Follow-up visits per routine care occur at approximately 1 week postoperatively for catheter removal, as well as at 1 month and 3 months. Appointments will follow routine scheduling practices for the office, which may include variance in exact visit timing. Generally, patients will have 1 week postoperative visit around 5-7 days after surgery, but may be delayed further by approximately 1 week depending on scheduling availability and/or clinical indication (e.g. need for cystogram). Follow-up visits are generally 1 month and 3 months post-surgery, but may occur approximately a couple weeks before or after as per physician standard of care scheduling to accommodate patient and physician availability. There will be no strict visit windows to allow for visit scheduling flexibility. Because the majority of RALP patients will be eligible for participation, schedulers will be educated on the importance of return visit timing accuracy. There will be no extended or long-term follow-up via direct patient contact or EMR review.

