Patients that are unable to pass gas while inpatient will be called on postoperative day 1 (if discharged same-day only) and day 2. The post-operative day 1 phone call will also be utilized to assess pain for those who were discharged same-day, as explained above. If a patient confirms that they have passed gas on day 1, they will not be called again on day 2. For Thursday/Friday procedures where days 1 and/or 2 (as applicable) fall on the weekend, patients will be called on Monday morning and asked to recall when they were able to pass gas (i.e., whether it occurred on Saturday or Sunday). If patients are not discharged same-day, they will only receive a single phone call on day 2 if they did not pass gas prior to discharge. Patients who are not discharged same-day and are able to pass gas prior to discharge will not receive any phone calls. In the case that a patient is still unable to pass gas on day 2, we will repeat phone calls daily until they are able to do so, although we do not anticipate many patients will need to be called past day 2. We are collecting this data due to recent anecdotal evidence in Robotic Urology that patients who receive Percocet were able to pass gas on average in 1.6 days versus 1.4 days for those that did not receive Percocet.

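### The coordinator who opens the randomization envelope also phones same-day-discharge patients for their final pain score, and the plan does not separate the two tasks

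*Combined protocol and SAP*

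**What the plan says.** Section 2.3 (Study Design) describes "randomization in a 1:1 single-blinded fashion" without saying who is blinded. The allocation schedule "will be hidden from the investigators until directly prior to surgery to prevent bias", and then "the CRC will open the randomization envelope in the operating room (OR) immediately prior to surgery".

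Table 2 gives the source of the last pain score as: "Recorded on the floor prior to discharge; OR via phone call by CRC for those discharged same-day". The text of section 2.3 after the table repeats this for day-0 discharges: "the CRC will call the following morning to evaluate pain". The paragraph on passing gas gives the call both purposes: "The post-operative day 1 phone call will also be utilized to assess pain for those who were discharged same-day".

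Section 2.4, under Aim 2, lists the final score, whether taken before discharge or by phone, among the time points to be compared between arms. Section 1.2 defines the pain score as a self-reported 0-10 numerical rating.

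**The concern.** The plan hides the allocation up to the moment of surgery in order to prevent bias, then lets the role that has just learned it collect a subjective outcome by conversation. The caller asks about five named body sites and any other site, and decides how to record a hesitant or vague answer. Someone who knows the arm can affect the result through prompting, tone or coding, even when the patient does not know the arm.

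Two features make this worth attention. Section 1.1 states the expectation of less pain at low pressure, so the caller knows which result is hoped for. And only same-day discharges are phoned, while section 1.1 also expects low pressure to allow a shorter stay and Aim 4 tests for it. The share of patients scored by an unblinded caller may therefore differ between arms. At stake is the credibility of the final Aim 2 comparison. Once the calls have been made, it cannot be repaired in the analysis.

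**Working it through.** **Step 1: who does what.** This is settled by reading the text.

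- Envelope opened in the operating room: the CRC (section 2.3).
- Phoned pain score for same-day discharges: the CRC (Table 2 and the text after it).
- Use of that score: final Aim 2 time point (section 2.4).
- Rule separating the tasks, second coordinator or blinded caller: none found.
- Routine inpatient scores: nursing staff (section 2.3).
- Added two-hourly study scores: the plan uses the first person plural and states neither role nor blinding status.

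Followed as written, the plan has the phoned score collected by a role that knows the arm.

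**Step 2: how much of Aim 2 is exposed.** The time points are PACU, first 4 hours on the floor, next 8 hours, following 8 hours, and the final score. The call supplies one of these five, and only in same-day discharges.

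**Step 3: the plan's own figure.** Section 2.4 gives means of 3.2 and 3.9 at 5-12 hours, SD 1.4, significance level 0.05 and 90% power. The effect size is 0.7/1.4 = 0.5. Two-sided, the normal approximation n = 2(1.960 + 1.282)² / 0.5² gives 84.1, so 85 per arm. The t-test solution is 85.03, so 86 per arm, as stated. Then 172/0.90 = 191.1, so 192, as stated. Changing who opens the envelope or makes the calls alters none of these inputs.

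**Step 4: can the bias be sized?** It needs the share phoned (f) and the shift caused by the caller (b). The plan gives neither. Purely as an illustration, assume:

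- no true difference in the final score;
- a shift b in phoned patients of one arm only;
- 86 patients per arm, and an SD of 1.4 borrowed from the 5-12 hour planning figures.

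The arm mean moves by d = f × b. The standard error is 1.4 × √(2/86) = 0.2135. The two-sided type I error is Φ(d/0.2135 − 1.96) + Φ(−d/0.2135 − 1.96).

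| Assumed b | f = 25% | f = 50% | f = 75% |
|---|---|---|---|
| 0.2 points | d = 0.05; 0.056 | d = 0.10; 0.075 | d = 0.15; 0.108 |
| 0.5 points | d = 0.125; 0.09 | d = 0.25; 0.22 | d = 0.375; 0.42 |

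The result runs from almost nothing to severe, depending entirely on two assumed numbers. The table shows that the documents cannot size the bias; it does not estimate it.

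**The case against.** The best reply is that the patient, not the coordinator, is the rater. The scale is a self-reported number, the patient is presumably the blinded party, and the caller only asks and records. The call has its own form (Appendix C), which is not in the text available for review, so its wording may already be scripted. Section 2.2 calls pain scores a secondary outcome. And the CRC is a role: two people might fill it. Most of this stands, and it limits the concern to interviewer influence. It does not remove the concern, because the plan requires no separation and a script would not hide the arm from the caller.

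Four stronger readings are tempting, and the documents do not support them:

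- **That the sample-size endpoint is affected.** The 5-12 hour score is not collected by this call. If the CRC also took the two-hourly scores, the exposure would be wider, but the plan does not say who takes them.
- **That the bias can be expressed as a share of the 0.7-point planning difference.** That difference belongs to the 5-12 hour interval. The plan gives no planning difference for the phoned score, so such a ratio has no defined meaning.
- **That any influence must favour 6 mmHg.** This is plausible given the stated hypothesis, but nothing in the documents establishes it.
- **That the repair is free.** Section 2.2 limits the forms and REDCap to designated study staff, and section 2.3 limits patient information to IRB-approved staff. The pressure data include the time and level of every adjustment and the time spent at each pressure. Handing that recording to an operating-room nurse takes real arrangement.

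**Conclusion.** The concern holds in a limited form. As written, someone who knows the arm collects a self-reported outcome by telephone, in a subset whose size may differ by arm. The possible harm is interviewer influence on one of five Aim 2 time points, and neither its size nor its direction can be established from the documents. The conclusion assumes that no unstated site practice separates the two tasks and that the patient is the party meant to be blinded. This is an inexpensive improvement worth making; it does not invalidate the trial or its sample size.

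**What to change.** Amend section 2.3 to state who is blinded, and to require that anyone who opens the envelope or sees the pressure data does not collect pain scores. Worded this way, the rule also covers the two-hourly inpatient scores, whose collector is not named. There are two ways to carry it out:

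1. Another of the already designated study staff, who has not seen the allocation, makes the day-1 calls from a fixed script. This is the simpler route.
2. A member of the operating-room team who must know the pressure anyway opens the envelope. Operating-room staff or the surgeon record the pressure fields, which stay hidden from the CRC until the 1-week data are entered.

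Both options need a short amendment and some scheduling of tasks. The second also needs the operating-room recorder to be designated as study staff, and the CRC's access to the pressure fields to be restricted on the paper forms and in REDCap, and possibly in the medical record.

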**Table 2. Post-operative pain monitoring schedule.**

Timeframe	Description	Time-Points	Pain Locations
During PACU stay	Upon admission to the PACU (typical stay of 1-2 hours)	PACU	Abdomen Legs
1 st 4 hours on the floor	Every 2 hours during the first 4 hours on the floor	Floor-0, 2, & 4 (hours 0 through 4)	Groin Scrotum
Next 8 hours on the floor	Every 2 hours during the next 8 hours on the floor	Floor-6, 8, 10, & 12 (hours 5 through 12)	Shoulder
Following 8 hours on the floor	Every 2 hours during the following 8 hours on the floor	Floor-14, 16, 18, & 20 (hours 13 through 20)	Other/specify
Final score immediately prior to discharge	Recorded on the floor prior to discharge; OR via phone call by CRC for those discharged same-day	Discharge, or Post-discharge	

1-Scores measured only while inpatient (or post-discharge for those discharged same-day) and awake; measures not taken in <1 hour from planned time will be marked as "missed."

Pain scores are measured using an 11-point numerical rating scale (NRS), in which a rating of 0 corresponds to no pain, 1-3 indicates mild pain, 4-6 indicates moderate pain, and 7-10 corresponds to severe pain. Scores are recorded by nursing staff as part of routine care in the PACU and on the postoperative recovery floor during the inpatient stay, however these measures are often not recorded in a consistent fashion with respect to timing. Therefore, we will record scores every 2 hours during the inpatient stay while the patient is awake (with the exception of the PACU, which occurs only at admission), and determine the average and maximum scores reported over sequential timeframes: during the PACU stay (typical stay of 1-2 hours), the first 4 hours on the floor, next 8 hours, and the following 8 hours; as well as the final score immediately prior to discharge (see Table 2). There will be no strict time window due to the variability of sleep schedules and discharge timing during the short inpatient stay, however, scores will be marked as "missed" if not recorded in <1 hour of the planned time. Pain will be measured with respect to the abdomen, legs, groin, scrotum, shoulder (due to insufflation), and "other" location. Pain medication morphine equivalents (MME) will also be measured over the same sequential timeframes during the inpatient stay through 1 week postoperatively. Patients

will be educated on the importance of bringing all medications to follow-up visits, which will lead to more accurate pain medication counts and calculations.

Patients are typically discharged on Day 0-1, and for those discharged on Day 0 (i.e., same-day), the CRC will call the following morning to evaluate pain (see Appendix C). Because we are targeting same-day or next-day discharge, there is the potential for missing data in the first 24-hour period. Therefore, there will be no restrictions or protocol deviations for pain scores, as we are collecting scores only while inpatient/awake and via phone call for those discharged same-day. Follow-up visits per routine care occur at approximately 1 week postoperatively for catheter removal, as well as at 1 month and 3 months. Appointments will follow routine scheduling practices for the office, which may include variance in exact visit timing. Generally, patients will have 1 week postoperative visit around 5-7 days after surgery, but may be delayed further by approximately 1 week depending on scheduling availability and/or clinical indication (e.g. need for cystogram). Follow-up visits are generally 1 month and 3 months post-surgery, but may occur approximately a couple weeks before or after as per physician standard of care scheduling to accommodate patient and physician availability. There will be no strict visit windows to allow for visit scheduling flexibility. Because the majority of RALP patients will be eligible for participation, schedulers will be educated on the importance of return visit timing accuracy. There will be no extended or long-term follow-up via direct patient contact or EMR review.

Patients that are unable to pass gas while inpatient will be called on postoperative day 1 (if discharged same-day only) and day 2. The post-operative day 1 phone call will also be utilized to assess pain for those who were discharged same-day, as explained above. If a patient confirms that they have passed gas on day 1, they will not be called again on day 2. For Thursday/Friday procedures where days 1 and/or 2 (as applicable) fall on the weekend, patients will be called on Monday morning and asked to recall when they were able to pass gas (i.e., whether it occurred on Saturday or Sunday). If patients are not discharged same-day, they will only receive a single phone call on day 2 if they did not pass gas prior to discharge. Patients who are not discharged same-day and are able to pass gas prior to discharge will not receive any phone calls. In the case that a patient is still unable to pass gas on day 2, we will repeat phone calls daily until they are able to do so, although we do not anticipate many patients will need to be called past day 2. We are collecting this data due to recent anecdotal evidence in Robotic Urology that patients who receive Percocet were able to pass gas on average in 1.6 days versus 1.4 days for those that did not receive Percocet.

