	

ii. Wound infection (y/n)

c. Length of stay (days; typically 0 to 1)

i. Discharge date/time (m-d-y; hh:mm)

3. Use of postoperative pain medication

a. Opioids (y/n for each: fentanyl, Dilaudid, oxycodone, Norco, tramadol, Percocet, Demerol)

i. Morphine equivalents (MME)

b. Non-opioids (y/n for each: Toradol, Tylenol, oxybutynin)

4. Postoperative pain scores (0-10; asleep, missed, or discharged)

a. Average and maximum scores during each interval (during the PACU stay, the first 4 hours on the floor, next 8 hours, and the following 8 hours; as well as the final score immediately prior to discharge)

b. At each location (abdomen, legs, groin, scrotum, shoulder, other/specify)

5. Timing of ability to pass gas (day 0, day 1, day 2, >day 2)

6. Clinically-significant ileus (i.e., requiring treatment; y/n)

Follow-Up (1 week, 1 month, & 3 months)	

1. QoR-15 (0-150) – only asked at week 1

a. Collected (y/n)

b. Score (0-150)

2. Prescription(s) given (y/n) – only asked at week 1

a. Prescription(s) filled (y/n)

b. Opioids (y/n for each: fentanyl, Dilaudid, oxycodone, Norco, tramadol, Percocet)

i. Number of pills taken for each (#)

ii. Morphine equivalents (MME)

c. Non-opioids (y/n for each: Toradol, Tylenol, oxybutynin)

3. Scrotal swelling (y/n) – only asked at week 1

4. Leg weakness (y/n)

a. Left, right, bilateral

b. Degree of weakness (each leg; mild, moderate, severe)

c. Impaired ability to walk

d. Impaired ability to drive

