## 2.4 – Statistical Analysis

The demographic and clinical characteristics of male patients age 18 or older with prostate cancer who are eligible and electing to undergo robotic assisted laparoscopic prostatectomy (RALP) at OhioHealth Dublin Methodist Hospital (DMH) Robotic Urology with the Principal Investigator will be reported using means and standard deviations or medians and interquartile ranges for continuous variables, or frequencies and percentages for categorical variables. We plan to compare the clinical outcomes of patients between different insufflation pressures (6 versus 15 mmHg). Continuous variables will be compared between two groups using independent sample t-test or Mann-Whitney U test, as appropriate, and categorical variables will be compared using Chi-square test or Fisher's exact test, as appropriate.

During the previous feasibility study of RALPs at an insufflation pressure of 6 mmHg, we found that there was a significant difference in pain scores at 5-12 hours. The average score in the 6 mmHg group was 3.2, and that in 15 mmHg historical group was 3.9. Using these values and an assumed standard deviation within each group of 1.4 (effect size = 0.5), at a significance level of 0.05 to achieve 90% power, the estimated sample size will be 86 patients in each group (total 172 patients). However, to account for ineligible patients after enrollment (estimated 10%), we will enroll minimum of 192 patients.

**Aim #1) Compare average postoperative pain medication use between groups, as measured in total morphine equivalents (MME) over time at pre-specified time intervals through follow-up at 1 week.**

Postoperative medication use between the two groups will be assessed at the following time points: during the PACU stay, during the first 4 hours on the floor, next 8 hours, the following 8 hours, and following discharge through the 1-week follow-up visit. Both total and average medication use measured in total morphine equivalents at/during each time point will be calculated and compared between two groups (6 versus 15 mmHg) using independent sample t-test or Mann-Whitney U test, as appropriate.

**Aim #2) Compare average and maximum postoperative pain scores between groups, as measured using the self-reported 11-point numerical rating scale (NRS), over time at pre-specified time intervals through discharge.**

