Similar to aim 1, postoperative pain scores will be assessed at following time points: during the PACU stay, during the first 4 hours on the floor, next 8 hours, and the following 8 hours, as well as the final scores immediately prior to discharge (or via phone call if discharged same-day). There will be only one measurement of pain at each bodily location during the PACU stay, as well as at discharge. However, the average and maximum postoperative pain scores will be calculated for each of the time intervals (the first 4 hours on the floor, next 8 hours, and the following 8 hours). The comparison of average and maximum scores at each time point between the two groups will be performed using independent sample t-test or Mann-Whitney U test, as appropriate.

The association between patient demographic or clinical characteristics and differences in medication use or pain scores will be assessed using multivariate regression. The appropriate type of regression (logistic or linear) used will be determined after data collection is complete.

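### The sample size rests on hours 5–12 pain, which same-day discharges can lack; power makes no allowance for this, and the planned test compares only patients with a reading

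*Combined protocol and SAP*

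**What the plan says.** - **Sizing (section 2.4).** The basis is a contrast between the feasibility patients and historical controls in pain at 5–12 hours: "The average score in the 6 mmHg group was 3.2, and that in 15 mmHg historical group was 3.9". With an assumed SD of 1.4, a 0.05 level and 90% power, this gives 86 per arm (172). Enrolment is raised to 192 for an estimated 10% found ineligible after enrolment.
- **The interval (section 2.3, Table 2).** It consists of "Floor-6, 8, 10, & 12 (hours 5 through 12" on the floor clock.
- **Collection (section 2.3).** "we are collecting scores only while inpatient/awake and via phone call for those discharged same-day". The plan foresees gaps: "Because we are targeting same-day or next-day discharge, there is the potential for missing data in the first 24-hour period". Its response is that absent scores will not count as deviations.
- **The phone call.** It is made the morning after a same-day discharge. Table 2 and Aim 2 in section 2.4 assign it to the final score, not to hours 5–12.
- **Recording (section 2.2, Table 1).** "Postoperative pain scores (0-10; asleep, missed, or discharged" are the permitted entries. Table 1 then lists averages and maxima per interval and location.
- **Analysis (section 2.4, Aim 2).** Average and maximum scores in each interval are compared by t-test or Mann-Whitney test. No analysis set is named.
- **Location (section 2.3).** "Pain will be measured with respect to the abdomen, legs, groin, scrotum, shoulder (due to insufflation" and an open category. Section 2.4 does not say which of these, or what combination, gave 3.2 and 3.9.
- **Status.** Section 2.2 calls pain scores a secondary outcome.

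**The concern.** Two things are at stake.

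The first is power. The 86 per arm must all have an hours 5–12 score, yet the plan targets discharges that can remove that score in whole or part. Nothing in the calculation allows for this.

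The second is comparability. A test on one interval can use only patients with at least one reading in it. That set depends on discharge, an event after randomisation. Section 1.1 expects low pressure to shorten the stay, and Aim 4 compares day 0 with day 1 discharge between arms. The comparison is then no longer the randomised one, and enrolling more patients would not change that.

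Two other comparisons share the problem. Aim 1 compares morphine equivalents over the same floor intervals; a patient who has gone home has no inpatient record for them, and use after discharge is a single period up to the 1-week visit. The final pain score mixes in-hospital readings with next-morning phone readings, in proportions set by discharge day.

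**Working it through.** **1. Reproduce the plan's figure.** Inputs from section 2.4: difference 3.9 − 3.2 = 0.7, SD 1.4, so d = 0.7/1.4 = 0.5; level 0.05; power 90%; 1:1 allocation (section 2.3). Sidedness is not stated. A two-sided two-sample t-test (noncentral t) needs 85.03, so 86 per arm, with power 0.903. A one-sided test would need 69, so two-sided is inferred. Inflation: 86/0.90 = 95.6, so 96 per arm and 192 in total. The arithmetic is correct for complete data.

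**2. Loss that 90% power can absorb.** 1 − 85.03/86 = 1.1% if 86 per arm are eligible; 1 − 85.03/96 = 11.4% if nobody proves ineligible.

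**3. Loss unrelated to pain.** The share f with no hours 5–12 reading is an assumption; the documents give no same-day rate or discharge hour. Power is that of the same t-test with n(1 − f) per arm.

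| f | from 86 per arm | from 96 per arm |
|---|---|---|
| 0 | 0.903 | 0.931 |
| 10% | 0.871 | 0.905 |
| 20% | 0.829 | 0.868 |
| 30% | 0.777 | 0.820 |
| 40% | 0.711 | 0.758 |

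**4. Partial readings.** If half of the same-day patients still give the hour 6 and hour 8 readings, simulated t-test power at 96 per arm is 84–87% for a 30–40% same-day share, and the observed difference is 0.68–0.70.

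**5. Loss related to early pain.** Simulation at 96 per arm: true hours 5–12 difference 0.70, SD 1.4, and lower early pain raising the odds of discharge (twofold per SD at 30% loss, threefold at 40%). The early-to-later correlation is assumed to be 0.7. Entries are the observed t-test difference and its power.

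| Early arm difference | 30% loss | 40% loss |
|---|---|---|
| 0 | 0.70, 83% | 0.70, 80% |
| 0.35 | 0.68, 81% | 0.66, 74% |
| 0.70 | 0.66, 79% | 0.61, 68% |

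The shrinkage is proportional to the correlation. In the bottom row it is 0.70 − 0.660 = 0.040 and 0.70 − 0.614 = 0.086. At a correlation of 0.3 it becomes 0.040 × 0.3/0.7 = 0.017 and 0.086 × 0.3/0.7 = 0.037, giving 0.68 and 0.66.

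**6. What a repeated-measures model recovers.** With the same discharge models at 96 per arm and 30–40% complete loss, model power is about 77–84% at correlation 0.3, 78–85% at 0.5 and 84–89% at 0.7. Its estimate stays near 0.70 if discharge depends only on observed early pain. If discharge also depends on later pain that was never observed, the model (at correlation about 0.7) gives 0.62–0.68 and the per-interval test 0.53–0.65.

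**The case against.** **The plan does handle missing scores.** It codes the reason, phones same-day patients and keeps patients who miss follow-up visits in the analysis. These do not close the gap. The codes concern recording, the call supplies a different time point, and the last rule is about later visits.

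**The size is unknown and may be small.** This stands. Step 4 shows a modest effect if same-day patients stay into the interval.

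**Bias is not shown.** This stands too. A reader might infer that early discharge will dilute the benefit of 6 mmHg. That needs conditions the documents do not state, such as lower-pain patients leaving first together with arms that already differ early. Section 1.1 mentions only appropriate criteria for same-day discharge, and section 2.4 reports a difference only at 5–12 hours. With no early difference and discharge driven by early pain alone, there is no shrinkage. The 0.70 may also already contain selection, since same-day discharge was allowed in the feasibility study.

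**A model is not clearly better.** Its gain rests on a correlation the documents do not give and is small at 0.3. Scores at some locations may be mostly zero, where a rank test suits better. This is why the planned tests are kept in support. It is also unproven that the individual readings will be in the database.

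**Sleep also removes readings.** This is true, and none of the figures above covers it.

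**Pain is secondary.** This limits the severity, but the stated power still rests on this score.

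**Conclusion.** The point holds as an omission in the power statement and the analysis. The 90% figure is correct only with essentially complete hours 5–12 data: up to about 1% loss at 86 per arm or 11% at 96. At an assumed 20–40% complete loss unrelated to pain, power is 83–71% or 87–76% respectively, and it is higher with partial readings. The per-interval comparison is restricted to a set selected by discharge.

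The documents do not establish that the trial is underpowered by any particular amount, or that the pain difference is biased. Shrinkage to about 0.61–0.68 requires the 0.70 early difference and the discharge model assumed in step 5, over correlations of 0.3–0.7. Aim 1's interval morphine equivalents have the same gap.

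This should be fixed, but it is not fatal, because pain is labelled secondary. Confidence is high on the omission and moderate on its size.

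**What to change.** 1. In section 2.4, restate power as a function of the number expected to have an hours 5–12 score, and name the location or combination that gave 3.2 and 3.9.
2. For that score, make the main analysis of average pain a repeated-measures mixed model on all scheduled readings (PACU and floor hours 0 to 20) of all randomised patients, with arm, time, arm-by-time and an unstructured or other pre-stated covariance. Report the hours 5–12 contrast. Keep the t-test or Mann-Whitney test as a supporting observed-case analysis, and for locations with mostly zero scores.
3. Add a sensitivity analysis that shifts hours 5–12 scores absent through discharge over a pre-stated range, including different shifts by arm. Report absent readings by arm and by reason (asleep, missed, discharged).
4. Report in-hospital and next-morning phone scores separately and descriptively, since each is a subset defined by discharge day. Do not use the phone score to fill hours 5–12.
5. State for Aim 1 how interval morphine equivalents are handled after a same-day discharge.

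**Cost.** This is mainly SAP wording, with no extra patients. If the database holds only the interval averages and maxima listed in Table 1, the individual readings must also be entered. The stated power becomes less favourable. The model relies on missing-at-random and restores power only in part (step 6), which is why the shift analysis is needed.
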